Cancers that become resistant to kinase inhibitors through a secondary mutation are still likely to be dependent on the activated kinase for their growth and survival. Thus, alternative strategies of inhibiting EGFR T790M may be therapeutically efficacious. This has prompted the preclinical and clinical development of second-generation irreversible EGFR inhibitors, such as BIBW 2992, which have shown activity in gefitinib-resistant preclinical models of NSCLC containing EGFR T790M. These irreversible TKIs are able to inhibit EGFR phosphorylation and lead to growth inhibition of cell lines and xenograft models containing EGFR T790M. Irreversible EGFR inhibitors are also ATP mimetics similar to gefitinib and erlotinib, but unlike gefitinib or erlotinib, they covalently bind Cys-797 of EGFR. How the irreversible nature of these agents allows them to inhibit EGFR phosphorylation is unclear. It is possible that by covalently binding to EGFR, the local concentration of these agents near the active site increases by several orders of magnitude (compared with gefitinib or erlotinib), thus providing a means of inhibiting EGFR phosphorylation despite the presence of a T790M mutation.

While the pre-clinical evidence for activity of BIBW 2992 in NSCLC with both activating EGFR mutations and T790M is promising, it remains unknown if BIBW 2992 can overcome the T790M mutation in lung cancer patients. This study will determine if treatment with BIBW 2992 prevents the acquisition of a T790M resistance mutation.

## **2.3 Molecular Techniques Background**

### **2.3.1 SNaPshot Genotyping Platform**

Recently, MGH implemented a multiplex molecular diagnostics platform (SNaPshot). This assay utilizes formalin-fixed paraffin-embedded tissue to quickly and economically identify 58 commonly mutated loci in 13 key oncogenes: EGFR, K-RAS, N-RAS, APC, BRAF, FLT3, JAK2, Kit, Notch, PI3K, PTEN, TP53, and beta-catenin. The DNA of interest is amplified using multiplexed PCR. Genotypes are determined using a single-base extension sequencing reaction, in which allele-specific probes interrogate loci of interest and are extended by fluorescently labeled dideoxynucleotides. The allele-specific probes have different sizes and are subsequently resolved by electrophoresis and analyzed by an automated DNA sequencer. Amplifications of EGFR, HER2, and MET and translocations in ALK are assessed using multicolor FISH assays. The SNaPshot profile has been validated and is performed in a CLIA-certified lab. It is used in place of routine EGFR and K-RAS mutation testing at our center, as it provides additional information that may be used to identify specific genetic abnormalities that correlate with tumor response to novel treatments.

Biopsies performed for this study at collaborating centers will undergo molecular analysis at MGH.

CONFIDENTIAL

This document is confidential. Do not disclose or use except as authorized.

### 2.3.2 Circulating Tumor Cell (CTC)-Chip

The ability to metastasize is one of the hallmarks of malignancy, and though its mechanisms are not fully described, circulating tumor cell (CTC) distribution through the bloodstream appears to be a vital step in the process. Successful capture and characterization of CTCs has tremendous potential as a vehicle to better understand the biology of the metastatic process, and provides an avenue to explore numerous clinical applications via non-invasive, patient-specific genomic analysis. Unlike tumor-derived cells in bone marrow, which can be dormant and long-lived, CTCs have a short half-life (<1 day) and their presence indicates a recent influx from an active proliferating tumor. Hence, CTCs may reflect the clinical status of cancer patients in a dynamic fashion, and could potentially be useful in the early detection of response to therapy.

At the MGH Cancer Center, investigators have developed a device called a “CTC-chip” to capture and quantify CTCs from patient blood samples. The CTC-chip is a microfluidic platform in which whole blood travels through a forest of micron-sized EpCAM antibody-coated microposts under precisely controlled laminar flow conditions. The arrangement and flow dynamics of the micropost array guides the cells gently through the chip and facilitates frequent interactions with the EpCAM antibody-coated microposts, resulting in capture of viable CTCs directly to the posts. We have demonstrated that the CTC-chip can attain successful capture of an average of 100 viable CTCs per mL of whole blood from 99% of tested advanced NSCLC patients, and that detection of EGFR mutations from isolated CTCs is feasible and correlates with tumor tissue sample testing. Furthermore, we showed that using an ultrasensitive allele-specific assay (the SARMS assay, by DXS) to look for EGFR mutations in the diagnostic tumor tissue samples, we identified a significant proportion of patients that had both activating EGFR mutations and low levels of detectable T790M. Though the T790M did not preclude a response to EGFR TKI therapy, it did correlate with a significantly shorter progression-free survival (7.7 months with detectable T790M compared to 16.5 months without, p<0.001). This is consistent with other studies suggesting that T790M is present at low levels in many EGFR mutant cancers, therefore therapy with an EGFR TKI that cannot inhibit T790M allows more rapid selective growth of the resistant clone.

Due to the nature of this technology (needs to be analyzed within hours of blood draw), only patients enrolled on this study at MGH will be able to submit samples for CTC analysis.

### 2.3.3 Interventional Radiology Repeat Biopsies

The MGH Department of Radiology provides sub-specialized care based on organ system. The Thoracic Imaging and Interventional Radiology section is directed by [name] and includes 13 providers, 6 of whom perform lung biopsies on a regular basis, totaling approximately 260 procedures per year. The thoracic service has a 4-slice multi-detector CT scanner specifically dedicated to thoracic interventional procedures. The Abdominal Imaging and Interventional Radiology section is directed by [name] and includes 20 providers, performing approximately 5000 procedures per year. The abdominal service has 3 fluoroscopic units, 2 helical CT scanners, and 2 ultrasound units specifically dedicated to abdominal intervention.

Since 2003, a total of 1719 lung/chest biopsies have been performed at MGH. Complications have included pneumothorax in 315 (18.3%), pneumothorax requiring chest tube in 43 (2.5%), and hemoptysis in 45 (2.6%). Mortality is very rare but may occur in patients with significant comorbidities. Since 2003 lung biopsies have resulted in death for only 1 patient (0.6%). These complication rates are comparable to those reported by other major academic centers.

CONFIDENTIAL

This document is confidential. Do not disclose or use except as authorized.

Over a 10-year period, 3559 liver biopsies have been performed under CT or ultrasound guidance at MGH by the GI/GU interventional radiology service; 1637 focal liver biopsies (where a focal mass was sampled) and 1922 nonfocal (where liver parenchyma was sampled for diffuse hepatic disease). Complications are categorized by the Society of Interventional Radiology criteria into three categories: 1) minor: no intervention needed or overnight admission for observation only; 2) major: requires therapy, > 48 hour hospital admission, prolonged hospitalization; or 3) death. Over a 10-year period, there were 32 complications (0.9%): 13 minor (0.3%), 17 major (0.5%), and 2 deaths (0.06%). Overall, the complication rate of biopsies at MGH by interventional radiology is low.

Interventional radiology services at collaborating institutions have similar experience and safety records.

## **2.4 Study Rationale**

As discussed above, NSCLC patients with EGFR mutations are highly likely to respond well to EGFR TK inhibition with either first-generation EGFR TKIs (erlotinib, geftinib) or with the second-generation irreversible inhibitor BIBW 2992, but resistance ultimately develops. Fifty percent of resistance to first-generation TKIs is due to the development of a secondary EGFR mutation in exon 20, the point mutation T790M. Though initially viewed as a clonal population arising in response to TKI therapy, newer research suggests that T790M is present in a small fraction of cells prior to treatment with first-generation TKIs (not detectable with standard bi-directional sequencing). Since the novel irreversible pan-HER inhibitor BIBW 2992 is highly active in lung cancers harboring activating EGFR mutations and can inhibit the EGFR T790M moiety in pre-clinical studies, a key question is whether BIBW 2992 can suppress the development of clinical resistance via T790M in lung cancer patients. The objectives of this pilot study are to estimate the effectiveness of BIBW 2992 at suppressing the development of the T790M resistance mutation in lung cancer patients. We will obtain a mandatory repeat tumor biopsy at the time of clinical progression and determine the proportion of patients that have a T790M mutation. This rate of mutation will be compared to the 50% historical data observed after development of resistance to reversible first-generation EGFR TKIs.

## **3. PARTICIPANT SELECTION**

### **3.1 Eligibility Criteria**

Participants must meet the following criteria on screening examination to be eligible to participate in the study:

- 3.1.1 Participants must have histologically or cytologically confirmed stage IIIB, IV, or recurrent non-small cell lung cancer
- 3.1.2 A somatic mutation in epidermal growth factor receptor (EGFR) must be present as documented by a CLIA-certified laboratory.
- 3.1.3 There must be radiographic measurable or evaluable disease
- 3.1.4 Participants must be willing, at the time of signing consent, to agree to a future biopsy of their tumor tissue at the time of disease progression, provided such a biopsy is safe and

CONFIDENTIAL

This document is confidential. Do not disclose or use except as authorized.

feasible at that time. This biopsy will be subjected to genetic analyses to attempt to identify the mechanism of acquired drug resistance.

- 3.1.5 Performance status must be 0, 1 or 2 on the Eastern Cooperative Oncology Group scale
- 3.1.6 Age must be  $\geq$  18 years
- 3.1.7 Participants must have normal organ and marrow function as defined below:
  - Absolute neutrophil count  $\geq$  1,500/mcL
  - Platelets  $\geq$  100,000/mcL
  - AST (SGOT)/ALT (SGPT)  $\leq$  3 X institutional upper limit of normal (ULN) or, if liver metastases present  $\leq$  5 X ULN
  - Total bilirubin  $\leq$  1.5 X ULN
  - Creatinine  $\leq$  1.5 X ULN or creatinine clearance  $\geq$  60 mL/min/1.73 m^2 for subjects with creatinine levels  $\geq$  1.5 x ULN
- 3.1.8 The effects of BIBW 2992 on the developing human fetus are unknown. For this reason, women of child-bearing potential and men must agree to use adequate contraception (hormonal or barrier method of birth control; abstinence) prior to study entry and for the duration of study participation. Should a woman become pregnant or suspect she is pregnant while participating in this study, she should inform her treating physician immediately.
- 3.1.9 Participants must have the ability to understand and the willingness to sign a written informed consent document.

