In oral repeated dose studies for up to 26 weeks in rats and minipigs, the main target organs were the gastrointestinal tract (rats and minipigs), kidneys (rat), and the skin (rats). In the gastrointestinal tract, increasing systemic exposure was associated with dose-dependent atrophy of the epithelium and concomitant focal erosions/ulcerations in the stomach of rats and minipigs. Clinically this resulted in diarrhea in both species and fecal occult blood in a single minipig. In rat kidneys papillary necrosis and dilated tubules were found. Similar pathologic findings, i.e., papillary necrosis in rats and dogs have been described previously for the EGFR-small molecule inhibitor gefitinib. However, nephrotoxicity has not been reported as a side-effect of gefitinib therapy in humans. A secondary pathophysiologic effect on renal function in BIBW 2992-treated animals due to diarrhea-induced dehydration and emaciation has to also be considered. Cutaneous alterations, i.e., epithelial atrophy were observed in rats. However, BIBW 2992 is not irritating to intact skin in albino rabbits and the effects observed in rats are most likely related to the specific pharmacodynamic mechanism of EGFR-inhibition (ref investigator's brochure). A variety of organs including the aerodigestive tract and reproductive organs were affected by epithelial atrophy. These atrophic changes were not severe and fully reversed during a 2-week recovery period. Minor cardiovascular effects (increased blood pressure and heart rate) and a dose-dependent decrease of QT time in the electrocardiogram (ECG) occurred in BIBW 2992-treated minipigs. These data do not indicate a risk for QT-prolongation related arrhythmia. BIBW 2992 had no pro-arrhythmic potential, as determined by the effects on HERG-mediated potassium current or on guinea pig papillary muscle action potential configuration. BIBW 2992 demonstrated mutagenic potential in bacteria but had no genotoxic potential *in vivo* even at highly toxic/lethal doses in animals. Because of its specific pharmacodynamic mechanism of action, BIBW 2992 is potentially embryo/fetotoxic and/or teratogenic.

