## **6.5 Contraception and Pregnancy**

Female patients who are not of childbearing potential due to being postmenopausal (2 years without menses) or surgical sterilization (oophorectomy, hysterectomy and/or tubal ligation) do not need to use contraception. All other female patients are considered to have childbearing potential and should use adequate contraception throughout the study (from screening until end of study participation or 28 days after last dose of trial medication, whichever is later).

Acceptable methods of contraception for females include hormonal contraception and double barrier method. Double barrier method of contraception is defined as two barrier methods used simultaneously each time the patient has intercourse. Accepted barrier methods include diaphragm, female condom, cervical cap, male condom and IUD (the diaphragm and cervical cap must be used in conjunction with spermicidal jelly/cream). If hormonal contraceptives are used, at least one barrier method should also be used. Partner vasectomy, natural 'rhythm' and spermicidal jelly/cream are not acceptable as methods of contraception.

Male patients should use adequate contraception throughout the study (e.g. condom and spermicidal jelly).

Female patients must have a negative pregnancy test ( $\beta$ -HCG test in urine or serum) prior to commencing study treatment. If a patient is found to be pregnant during study participation, this should be handled as follows:

CONFIDENTIAL

This document is confidential. Do not disclose or use except as authorized.

Timing of Pregnancy	Action
Prior to starting study medication	Patient should be withdrawn from the study immediately. No reporting necessary.
During study treatment	Treatment must be stopped immediately and the pregnancy should be reported immediately using the pregnancy form.  If the investigator wishes to give any further treatment with study medication, this must be discussed and agreed with Boehringer Ingelheim.

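### For women of child-bearing potential, Section 3.1.8 accepts a single contraceptive method that Section 6.5 does not, and the two sections can also differ on how long contraception must last.

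*Combined protocol and SAP*

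**What the plan says.** Three parts of the combined protocol and SAP bear on this.

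- **Section 3.1.8 (Eligibility Criteria)** covers women of child-bearing potential and men together. It gives the accepted methods in parentheses as "hormonal or barrier method of birth control; abstinence" and the period as "prior to study entry and for the duration of study participation". The reason it gives is "The effects of BIBW 2992 on the developing human fetus are unknown". It does not refer to Section 6.5.
- **Section 6.5 (Contraception and Pregnancy)** states for women: "Acceptable methods of contraception for females include hormonal contraception and double barrier method". It then adds: "If hormonal contraceptives are used, at least one barrier method should also be used". On barriers it says: "Double barrier method of contraception is defined as two barrier methods used simultaneously each time the patient has intercourse". The period for women is "from screening until end of study participation or 28 days after last dose of trial medication, whichever is later". For men it asks for adequate contraception throughout the study, gives a condom with spermicidal jelly as an example, and states no period after the last dose.
- **Section 2.1.2 (Pharmacology and Toxicology Profile)** says, on the basis of the drug's mechanism, that "BIBW 2992 is potentially embryo/fetotoxic and/or teratogenic".

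The pregnancy table in Section 6.5 also provides for a pregnancy within 28 days of the last dose in a woman who has already left the study. The protocol thus foresees that participation can end before that date.

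**The concern.** Section 3.1.8 carries its own complete definition, and the word *or* makes one method enough. Someone screening a patient has no cue to look further. Section 6.5 does more than add detail for women, because it declines a hormonal method alone and a single barrier alone, both of which 3.1.8 accepts.

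Entry runs on Section 3. Section 4.2 makes registration depend on the eligibility checklist, Appendix 3 (4.10.1) says that the checklist sets out the eligibility criteria, and Section 5.8.1 makes the first dose depend only on meeting those criteria. With several participating institutions, sites may also apply different rules.

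What is at stake is fetal exposure to a drug for which the protocol itself flags a reproductive risk. No estimate or test in the trial depends on it.

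**Working it through.** The plan states no figure on this point, so there is nothing to reproduce. The check sets the texts side by side and applies both rules to each kind of participant.

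**Method**

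| Participant | Section 3.1.8 | Section 6.5 |
|---|---|---|
| Woman, hormonal method only | Accepted | Not sufficient: a barrier must be added |
| Woman, one barrier only | Accepted | Not sufficient: barrier contraception is described as two barriers together |
| Woman, hormonal plus a barrier | Accepted | Accepted |
| Woman, two barriers together | Accepted | Accepted |
| Woman, abstinent | Accepted | Neither listed nor excluded |
| Man, one barrier | Accepted | Adequate contraception required; a two-part method is given only as an example |

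The first two rows contradict each other. The abstinence row is a silence. The row for men is an imprecision.

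**Duration (women)**

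Let *d* be the number of days from the last dose to the end of study participation.

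- Under 3.1.8 the obligation ends on day *d*.
- Under 6.5 it ends on day max(*d*, 28).
- The difference is max(0, 28 − *d*) days.

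If participation ends with the last dose, *d* = 0 and the difference is 28 days, the largest possible. If *d* is 28 or more, the difference is 0.

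Section 7.1.4 calls for a clinic visit at least 30 days after the repeat biopsy. For a woman whose last dose falls on or before the day of the biopsy, and whose participation is taken to run to that visit, *d* is at least 30 and there is no gap. A gap can arise for a woman who leaves without a biopsy, because Section 7.1 makes the biopsy optional when treatment stops for a reason other than progression.

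**Stated risk**

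Section 3.1.8 calls the fetal effects unknown, while 2.1.2 calls the drug potentially harmful to the embryo or fetus. The two can be read together, since effects in humans may be unknown while a hazard is expected from the mechanism. Even so, the section used at entry carries the weaker statement.

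**The case against.** The best defence is that 3.1.8 is a summary and 6.5 is the operating rule. For women, 6.5 applies from screening, so it is already in force at entry. A woman who follows 6.5 also satisfies 3.1.8, so both rules can be met at once. Criterion 3.2.10 excludes anyone unable to comply with the protocol, which includes 6.5.

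This does not remove the conflict. Criterion 3.2.10 concerns inability, and does not catch a woman who could comply with 6.5 but was told only the rule in 3.1.8. That 6.5 starts at screening does not help a site that is working from a self-contained criterion with no cross-reference.

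Other safeguards limit the consequence. Pregnancy is an exclusion (3.2.9), a negative test is required before treatment (6.5), suspected pregnancy must be reported at once (3.1.8), and treatment stops if pregnancy occurs (6.5). These points stand. They reduce the harm that the mismatch could cause, but they leave the mismatch in place.

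A reader might infer more than the text supports in five respects:

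- **That 6.5 rules out abstinence.** It introduces its accepted methods as examples, names several unacceptable ones without naming abstinence, and ties the double-barrier rule to intercourse. It is silent on abstinence.
- **That every enrolled woman of child-bearing potential is affected.** A woman using combined methods meets both sections on method.
- **That contraception always ends 28 days too early under 3.1.8.** The gap depends on when participation ends, and 28 days is its maximum.
- **That the combined-method rule and the 28-day period bind men.** Both are written for women.
- **That the consent form repeats 3.1.8.** The consent pages are not among the documents reviewed, so this cannot be checked.

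**Conclusion.** The point holds for women of child-bearing potential. On method the contradiction is direct: one hormonal or one barrier method satisfies 3.1.8 and fails 6.5. On duration it is conditional: the sections differ only when participation ends less than 28 days after the last dose, and then by 28 − *d* days.

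The number of women concerned cannot be estimated. The documents give a planned enrolment of 20 (Section 1.1) or 24 (Section 12.1) and no breakdown by sex, child-bearing potential or contraceptive method.

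The method conflict rests on the wording alone. The duration point assumes that participation can end within 28 days of the last dose, which the pregnancy table in 6.5 recognises. The argument about entry assumes that the checklist, which is not reproduced, carries the wording of 3.1.8, as Appendix 3 (4.10.1) indicates.

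This is a drafting inconsistency with a bearing on participant safety. It should be corrected, but it does not touch the T790M endpoint, the power calculation or any analysis. Nothing here says which contraceptive rule is right.

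**What to change.** Reconcile Sections 2.1.2, 3.1.8 and 6.5, including the pregnancy table in 6.5, so that the protocol carries:

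- one list of accepted methods for women, stating whether a single method suffices and whether abstinence is accepted;
- one duration for women, with the end of the period defined relative to the last dose and to the end of participation;
- an explicit rule for men on both method and duration;
- one consistent statement of fetal risk.

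Section 3.1.8 should cross-refer to 6.5, and the eligibility checklist should use the same text. The consent form should be checked against the result. The clinical team decides which rule stands.

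The cost is a one-paragraph amendment and a checklist update. Nothing in the sample size or the analysis changes.

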## **3.2 Exclusion Criteria**

Participants who exhibit any of the following conditions at screening will not be eligible for admission into the study.

- 3.2.1 Prior EGFR tyrosine kinase inhibitor therapy (including gefitinib, erlotinib, or any experimental EGFR TKI agents)
- 3.2.2 Known brain metastases, unless they have undergone definitive therapy and are neurologically stable at the time of study entry
- 3.2.3 Standard chemotherapy or radiation  $\leq$  2 weeks of starting BIBW 2992, or experimental systemic cancer therapy  $\leq$  4 weeks of starting BIBW 2992. Note that prior palliative radiation to bony disease, CNS disease, or a limited thoracic area is only allowed if there is measurable or progressive disease outside the field of radiation.
- 3.2.4 Another malignancy within the last 3 years (except non-melanoma skin cancer or a non-invasive/*in situ* cancer)
- 3.2.5 Known pre-existing and clinically active interstitial lung disease

CONFIDENTIAL

This document is confidential. Do not disclose or use except as authorized.

- 3.2.6 Significant gastrointestinal disorders with diarrhea as a major symptom (e.g. Crohn's disease, malabsorption, etc)
- 3.2.7 History of clinically relevant cardiovascular abnormalities such as uncontrolled hypertension, congestive heart failure NYHA classification of 3, unstable angina or poorly controlled arrhythmia, or myocardial infarction within 6 months.
- 3.2.8 Any other concomitant serious illness or organ system dysfunction which in the opinion of the investigator would either compromise patient safety or interfere with the evaluation of the safety of the study drug.
- 3.2.9 Pregnancy or breast feeding.
- 3.2.10 Inability to comply with the protocol
- 3.2.11 Participants may not be receiving any other investigational agents during the course of BIBW 2992 therapy.
- 3.2.12 History of allergic reactions attributed to compounds of similar chemical or biologic composition to BIBW 2992.
- 3.2.13 Life expectancy < 12 weeks

